## **16 DATA COLLECTION, RETENTION AND MONITORING**

### **16.1 Data Collection Instruments**

The Investigator will prepare and maintain adequate and accurate source documents designed to record all observations and other pertinent data for each subject treated with the study drug.

Study personnel at each site will enter data from source documents corresponding to a subject's visit into the protocol-specific electronic Case Report Form (eCRF) or paper CRF when the information corresponding to that visit is available. Subjects will not be identified by name in the study database or on any study documents to be collected by the Investigator (or designee) but will be identified by their unique PID.

For eCRFs: If a correction is required for an eCRF, the time and date stamps track the person entering or updating eCRF data and creates an electronic audit trail. For paper CRFs: If a correction is made on a CRF, the study staff member will line through the incorrect data, write in the correct data and initial and date the change.

The Investigator is responsible for all information collected on subjects enrolled in this study. All data collected during the course of this study must be reviewed and verified for completeness and accuracy by the Investigator.

### **16.2 Data Management Procedures**

The data will be entered into a validated database (REDCap). The Data Management group will be responsible for data processing, in accordance with procedural documentation.

All procedures for the handling and analysis of data will be conducted using good computing practices meeting FDA guidelines for the handling and analysis of data for clinical trials.

### **16.3 Data Quality Control and Reporting**

After data have been entered into the study database, a system of computerized data validation checks will be implemented and applied to the database on a regular basis. Query reports (Data Clarification Requests) pertaining to data omissions and discrepancies will be forwarded to the study team for resolution. The study database will be updated in accordance with the resolved queries.

### **16.4 Archival of Data**

The database is safeguarded against unauthorized access by established security procedures; appropriate backup copies of the database and related software files will be maintained. Databases are backed up by the database administrator in conjunction with any updates or changes to the database.

At critical junctures of the protocol (e.g., production of interim reports and final reports), data is cleaned per established procedures.

### **16.5 Availability and Retention of Investigational Records**

The Investigator must make study data accessible to the monitor, IRB/IEC, and Regulatory Agency (e.g., FDA) inspectors upon request. A file for each subject must be maintained that includes the signed Informed Consent, HIPAA Authorization and Assent Form and copies of all source documentation related to that subject. The Investigator must ensure the reliability and availability of source documents from which the information on the CRF was derived.

All study documents (patient files, signed informed consent forms, copies of CRFs, Study File Notebook, etc.) must be kept secured for a period of two years following marketing of the investigational product or for two years after centers have been notified that the IND has been discontinued. There may be other circumstances for which the Investigator is required to maintain study records and, therefore, the Investigator should be contacted prior to removing study records for any reason.

As outlined above, after completion of the primary analyses, samples may be stored indefinitely via the LIINC biorepository for use on other COVID-related pathogenesis studies (as addressed in the consent form), at the discretion of the PI.

## **16.6 Monitoring**

Monitoring visits will be conducted by representatives of the Investigator according to the U.S. CFR Title 21 Parts 50, 56, and 312 and ICH Guidelines for GCP (E6). By signing this protocol, the Investigator grants permission to the monitor, and appropriate regulatory authorities to conduct on-site monitoring and/or auditing of all appropriate study documentation.

## **16.7 Subject Confidentiality**

In order to maintain subject confidentiality, only a subject PID will identify all study subjects on CRFs and other documentation. Additional subject confidentiality issues (if applicable) are covered in the Clinical Study Agreement.

# **17 ADMINISTRATIVE, ETHICAL, REGULATORY CONSIDERATIONS**

The study will be conducted according to the Declaration of Helsinki, Protection of Human Volunteers (21 CFR 50), Institutional Review Boards (21 CFR 56), and Obligations of Clinical Investigators (21 CFR 312).

To maintain confidentiality, all laboratory specimens, evaluation forms, reports and other records will be identified by a coded number and initials only. All study records will be kept in a locked file cabinet and code sheets linking a patient's name to a patient identification number will be stored separately in another locked file cabinet. Clinical information will not be released without written permission of the subject, except as necessary for monitoring by the FDA. The Investigator must also comply with all applicable privacy regulations (e.g., Health Insurance Portability and Accountability Act of 1996, EU Data Protection Directive 95/46/EC).

## **17.1 Protocol Amendments**

Any amendment to the protocol will be written by the Investigator or their designee. Protocol amendments cannot be implemented without prior written IRB/IEC approval except as necessary to eliminate immediate safety hazards to patients. A protocol amendment intended to eliminate an apparent immediate hazard to patients may be implemented immediately, provided the IRBs are notified within five working days.

## **17.2 Institutional Review Boards and Independent Ethics Committees**

The protocol and consent form will be reviewed and approved by the IRB/IEC of each participating center prior to study initiation. Serious adverse experiences regardless of causality will be reported to the IRB/IEC in accordance with the standard operating procedures and policies of the IRB/IEC, and the Investigator will keep the IRB/IEC informed as to the progress of the study. The Investigator will obtain assurance of IRB/IEC compliance with regulations.

Any documents that the IRB/IEC may need to fulfill its responsibilities (such as protocol, protocol amendments, Investigator's Brochure, consent forms, information concerning patient recruitment, payment or compensation procedures, or other pertinent information) will be submitted to the IRB/IEC. The IRB/IECs written unconditional approval of the study protocol and the informed consent form will be in the possession of the Investigator before the study is initiated. The IRB/IECs approval statement will be transmitted by the Investigator to Aerium Therapeutics. This approval must refer to the study by exact protocol title and number and should identify the documents reviewed and the date of review.

Protocol and/or informed consent modifications or changes may not be initiated without prior written IRB/IEC approval except when necessary to eliminate immediate hazards to the patients or when the change(s) involves only logistical or administrative aspects of the study. Such modifications will be submitted to the IRB/IEC and written verification that the modification was submitted and subsequently approved should be obtained.

The IRB/IEC must be informed of revisions to other documents originally submitted for review; serious and/or unexpected adverse experiences occurring during the study in accordance with the standard operating procedures and policies of the IRB; new information that may affect adversely the safety of the patients of the conduct of the study; an annual update and/or request for re-approval; and when the study has been completed.

### **17.3 Informed Consent Form**

Informed consent will be obtained in accordance with the Declaration of Helsinki, ICH GCP, US Code of Federal Regulations for Protection of Human Subjects (21 CFR 50.25[a,b], CFR 50.27, and CFR Part 56, Subpart A), the Health Insurance Portability and Accountability Act (HIPAA, if applicable), and local regulations.

The Investigator will prepare the informed consent form and HIPAA authorization for submission to the IRB/IEC. The consent form generated by the Investigator must be approved by the IRB/IEC. The written consent document will embody the elements of informed consent as described in the International Conference on Harmonisation and will also comply with local regulations. The Investigator will store an IRB/IEC-approved copy of the Informed Consent Form for the study file.

A properly executed, written, informed consent will be obtained from each subject prior to entering the subject into the trial. Information should be given in both oral and written form and subjects (or their legal representatives) must be given ample opportunity to inquire about details of the study. If appropriate and required by the local IRB/IEC, assent from the subject will also be obtained. If a subject is unable to sign the informed consent form (ICF) and the HIPAA authorization, a legal representative may sign for the subject. A copy of the signed consent form will be offered to the subject or legal representative of the subject and the original will be maintained with the subject's records.

### **17.4 Publications**

The preparation and submittal for publication of manuscripts containing the study results shall be in accordance with a process determined by mutual written agreement among the study Investigator and participating institutions. The publication or presentation of any study results shall comply with all applicable privacy laws, including, but not limited to, the Health Insurance Portability and Accountability Act of 1996.

### **17.5 Investigator Responsibilities**

By signing the Agreement of Investigator form, the Investigator agrees to:

1. Conduct the study in accordance with the protocol and only make changes after notifying Aerium Therapeutics, except when to protect the safety, rights or welfare of subjects.

2. Personally conduct or supervise the study (or investigation).
3. Ensure that the requirements relating to obtaining informed consent and IRB review and approval meet federal guidelines, as stated in § 21 CFR, parts 50 and 56.
4. Report to Aerium Therapeutics or designee any AEs that occur in the course of the study, in accordance with §21 CFR 312.64.
5. Ensure that all associates, colleagues and employees assisting in the conduct of the study are informed about their obligations in meeting the above commitments.
6. Maintain adequate and accurate records in accordance with §21 CFR 312.62 and to make those records available for inspection with the Aerium Therapeutics (or designee).
7. Ensure that an IRB that complies with the requirements of §21 CFR part 56 will be responsible for initial and continuing review and approval of the clinical study.
8. Promptly report to the IRB and Aerium Therapeutics (or designee) all changes in the research activity and all unanticipated problems involving risks to subjects or others (to include amendments and IND safety reports).
9. Seek IRB approval before any changes are made in the research study, except when necessary to eliminate hazards to the patients/subjects.
10. Comply with all other requirements regarding the obligations of clinical investigators and all other pertinent requirements listed in § 21 CFR part 312.

## APPENDIX 1. SCHEDULE OF EVENTS

Target Day	-28	-7	0	1	15	30	90	180	360
Visit Name	Screen	Baseline	Intervention	Phone FU	2W	1M	3M	6M	12M
Visit Window	-28 to -8	-21 to -1	N/A	+1	+/-3	+/-5	+/-14	+/-14	+/-28
Screening Procedures									
Informed Consent	x								
Eligibility Review	x								
Screening Labs	x								
Demographics	x								
Medical History (inc. ME/CFS, hEDS, EM, MCAS assess.)	x								
COVID-19 History	x								
Concomitant Medications	x	x	x	x	x	x	x	x	x
Study Product Administration									
Randomization			x						
AER002 vs Placebo			x						
Clinical Assessments									
Vital Signs	x	x	x 		x	x	x	x	x
Physical Assessment	x	PRN	PRN		PRN	PRN	PRN	PRN	PRN
Long COVID Symptom Assessment (LIINC Quest.)	x	x	x		x	x	x	x	x
Quality of Life, (e.g., EuroQoL)	x	x			x	x	x	x	x
PROMIS-29	x	x			x	x	x	x	x
PGIC Scale						x	x	x	x
Duke Activity Status Index	x	x			x	x	x	x	x
Post-COVID Functional Scale	x	x			x	x	x	x	x
Dysautonomia Assessment (e.g., COMPASS-31)		x					x	x	x

Target Day	-28	-7	0	1	15	30	90	180	360
Visit Name	Screen	Baseline	Intervention	Phone FU	2W	1M	3M	6M	12M
Visit Window	-28 to -8	-21 to -1	N/A	+1	+/-3	+/-5	+/-14	+/-14	+/-28
DSQ-PEM		x		x	x	x	x	x	x
WHO-DAS		x					x	x	x
Neurocognitive assessment (e.g., NIH Toolbox)		x					x	x	x
6MWT		x			x	x	x	x	x
Safety Outcomes									
AE Review	x	x	x	x	x	x	x	x	x
Safety Labs			x		x				
Real-time laboratory tests									
Pregnancy testing	x		x				x		
Complete metabolic panel	x		x		x				
CBC/diff	x		x		x				
Coagulation studies Within 6 months of Screen	x								
Hep B surface antigen Within 6 months of Screen	x								
Hep C antibody Within 6 months of Screen	x								
Hep C RNA (if Ab positive) Within 6 months of Screen	x								
Plasma HIV RNA (if HIV+) Within 2 months of Screen	x								
C-reactive protein		x	x		x	x	x	x	x
Erythrocyte sedimentation rate		x	x		x	x	x	x	x
D-dimer		x	x		x	x	x	x	x
Fibrinogen		x	x		x	x	x	x	x
SARS-CoV-2 PCR or Ag test	x	PRN	PRN		PRN	PRN	PRN	PRN	PRN
Stool collection (optional)		x				x		x	x

Target Day	-28	-7	0	1	15	30	90	180	360
Visit Name	Screen	Baseline	Intervention	Phone FU	2W	1M	3M	6M	12M
Visit Window	-28 to -8	-21 to -1	N/A	+1	+/-3	+/-5	+/-14	+/-14	+/-28
Post-hoc laboratory tests									
SARS-CoV-2 antibody testing		x							
Biospecimen storage	x	x	x		x	x	x	x	x
Markers of viral persistence	x	x	x		x	x	x	x	x
Markers of inflammation		x	x		x	x	x	x	x
PK analyses 			x 		x	x	x	x	x
ADA Immunogenicity 			x		x	x	x	x 	x 
SARS-CoV-2 PCR/Genotyping	x		x		x	x	x	x	x

 Performed pre-dose and post-dose

 Collected pre-dose and 1 hour +/- 10 minutes post dose

 Continue to collect if ADA is detected at previous visit

 PK and ADA post dose sample collection windows:

- D15 (acceptable +/- 3 Days)
- D30 (acceptable +/- 5 Days)
- D90 (acceptable +/- 14 Days)
- D180 (acceptable +/- 14 Days)
- D360 (acceptable +/- 28 Days)

Abbreviations: myalgic encephalomyelitis/chronic fatigue syndrome, ME/CFS; hypermobile Ehler-Danlos Syndrome, hEDS; endometriosis, EM; mast cell activation syndrome, MCAS; DePaul Symptom Questionnaire-Post-Exertional Malaise, DSQ-PEM; postural orthostatic tachycardia syndrome, POTS; pharmacokinetic, PK; anti-drug antibody, ADA.

**APPENDIX 2. NIH COVID-19 TREATMENT GUIDELINES DEFINITION OF MODERATE OR SEVERE IMMUNOCOMPROMISE, MARCH 6, 2023**

- Are receiving active treatment for solid tumor and hematologic malignancies.
- Have hematologic malignancies (e.g., chronic lymphocytic lymphoma, non-Hodgkin lymphoma, multiple myeloma, acute leukemia) and are known to have poor responses to COVID-19 vaccines or an increased risk of severe COVID-19, regardless of the treatment status for the hematologic malignancy.
- Received a solid-organ or islet transplant and are receiving immunosuppressive therapy.
- Received chimeric antigen receptor T cell (CAR T-cell) therapy or a hematopoietic cell transplant (HCT) and are within 2 years of transplantation or are receiving immunosuppressive therapy.
- Have a moderate or severe primary immunodeficiency (e.g., severe combined immunodeficiency, DiGeorge syndrome, Wiskott-Aldrich syndrome, common variable immunodeficiency disease).
- Have advanced or untreated HIV infection (defined as people with HIV and CD4 T lymphocyte [CD4] cell counts <200 cells/mm^3, a history of an AIDS-defining illness without immune reconstitution, or clinical manifestations of symptomatic HIV).
- Are receiving active treatment with high-dose corticosteroids (i.e., ≥20 mg prednisone or equivalent per day when administered for ≥2 weeks), alkylating agents, antimetabolites, transplant-related immunosuppressive drugs, cancer chemotherapeutic agents classified as severely immunosuppressive, or immunosuppressive or immunomodulatory biologic agents (e.g., B cell–depleting agents).

**APPENDIX 3. HOME-BASED ACUTE COVID-19 RESEARCH PROTOCOL**

Participants who test positive during the study will be referred for participation in a home-based acute COVID-19 research protocol. That protocol is outlined below.

Time since onset of symptoms	DE	D3	D4	D5	D6	D7	D8	D9	D10	D11	D12	D13	D14	D17	D19	D21	D28
In-person study visits	x	x	x	x									x				x
Baseline survey	x	x	x	x													
Follow-up survey								x					x				x
Clinical antibody	x	x	x	x													x
Nasal swab	x	x	x	x	x	x	x	x	x	x	x	x	x	x	x	x	x
Rapid Antigen Test	x	x	x	x	x	x	x	x	x	x	x	x	x	x	x	x	x

\*DE, day of enrollment.

## APPENDIX 4. PROTOCOL AMENDMENTS

Date	Version	Section	Changes
2023-MAR-01	1.0	N/A	N/A
2023-MAR-24	1.1	N/A	Addressed initial IRB stipulations
2023-APR-24	1.2	N/A	Addressed FDA suggestions
2023-JUN-24	1.3	N/A	Addressed FDA suggestions Addressed Patient-Led Research Collaborative suggestions Corrected various typos
2023-JUN-24	1.3	2.3.1	Clarified that participants will be screened for signs and symptoms of anemia and tested as outlined in the Schedule of Events (unchanged)
2023-JUN-24	1.3	2.3.1	Clarified that participants will be screened for signs and symptoms of anemia and tested as outlined in the Schedule of Events (unchanged)
2023-JUN-24	1.3	5.1	Added DSQ-PEM as outcome
2023-JUN-24	1.3	6.2	Clarified that by "index SARS-CoV-2 infection" we mean "SARS-CoV-2 infection to which Long COVID is attributed" Deleted "with persistent viral shedding from nasopharynx" at suggestion of FDA
2023-JUN-24	1.3	6.3	Clarified exclusion related to other investigational products, specifically PET tracers which have a short half-life and no biological activity outside this window. Clarified exclusion criteria related to current cardiovascular disease

			Clarified exclusion criteria related to prior ME/CFS and dysautonomia
2023-JUN-24	1.3	9.1.3	Clarified that medical history may include screening for related conditions such as ME/CFS, POTS, hypermobility syndromes, endometriosis, and mast cell activation syndrome.
2023-JUN-24	1.3	9.1.6	Added additional instruments that will be used to assess medical history and outcomes at recommendation of Patient Led Research Collaborative  Added additional detail about the approach to recording Long COVID Symptoms and other symptoms (AE Review) as adverse events.  Added clarification about neurocognitive testing.
2023-JUN-24	1.3	9.2.7	Clarified that quantifiable HIV refers to values >48 copies/mL
2023-JUN-24	1.3	10.1	Added clarification that the screening procedures may be conducted over time if need be to reduce participant burden  Added clarification about medical history at screening visit
2023-JUN-24	1.3	10.2	Added option to complete Screening and Baseline assessments over multiple visits if needed to reduce participant burden
2023-JUN-24	1.3	10.5	Corrected “D14” error to “D15” to match schedule of events
2023-AUG-18	1.4	5.1	Indicated that Dysautonomia Assessment could be COMPASS-31 or a similar scale. This is because there might be licensing issues related to COMPASS-31.

2023-AUG-18	1.4	6.2	Corrected criterion 8 to indicate "In otherwise stable health prior to Screen" rather than "D0" since eligibility for the protocol must be determined prior to D0. Additionally edited criteria 4, 5, 7, 8, 9, and 23 to anchor on planned D0, since eligibility needs to be determined prior to D0. Added in section 10.3 that prior to infusion, participants will be queried prior to infusion regarding any major health changes related to these criteria and any major changes to health will be discussed with a study clinician to confirm whether the infusion should proceed.
2023-AUG-18	1.4	9.1.4	Corrected discrepancy regarding who is allowed to conduct the screening physical examination, to make consistent with section 10.1. A qualified study clinician (physician, nurse, or physician assistant) may conduct this examination.
2023-AUG-18	1.4	9.1.6	Indicated that Dysautonomia Assessment could be COMPASS-31 or a similar scale. This is because there might be licensing issues related to COMPASS-31.
2023-AUG-18	1.4	10.3	Edited as per item 6.2 above to include confirmation of no major health changes prior to infusion.
2023-AUG-18	1.4	10.4	Added DSQ-PEM at the time of the phone follow-up.
2023-AUG-18	1.4	SOE	Indicated that Dysautonomia Assessment could be COMPASS-31 or a similar scale. This is because there might be licensing issues related to COMPASS-31.
2023-AUG-18	1.4	SOE	Indicated that the DSQ-PEM would be administered at the phone follow-up at 1M visit
2023-NOV-16	1.5	10.1	Specified that rescreening can occur.
2023-NOV-16	1.5	SOE	Removed Long COVID symptom assessment from the D1 phone follow-up. Note: The AE assessment and DSQ-PEM (post-exertional malaise) questionnaire still take place at this time point, but there is no need to ascertain Long COVID symptoms at this time point.

2023-NOV-16	1.5	SOE	Added DSQ-PEM to 2W assessment (SMC recommendation)
2023-NOV-16	1.5	SOE	Added PGIC scale at 3-, 6-, and 12-month timepoints.

UNIVERSITY OF CALIFORNIA, SAN FRANCISCO

**AN EXPLORATORY, RANDOMIZED, DOUBLE-BLIND PLACEBO-CONTROLLED STUDY TO  
ASSESS THE SAFETY OF AN ANTI-SARS-COV-2 MONOCLONAL ANTIBODY AND  
RESPONSE TO TREATMENT IN INDIVIDUALS WITH LONG COVID (OUTSMART-LC)  
(COVID-19)**

NCT05877508

Statistical Analysis Plan Document Date: 11DEC2024

## 1. Introduction

The objective of this statistical analysis plan (SAP) is to describe the general analytic strategy and the statistical methods that will be used to analyze the data for [NCT05877508](#) - "An Exploratory, Randomized, Double-Blind Placebo-Controlled Study to Assess the Safety of An Anti-SARS-CoV-2 Monoclonal Antibody and Response to Treatment in Individuals With Long COVID" (OUTSMART-LC).

## 2. Study Design

### 2.1. Randomization and Follow-Up

This is an exploratory, 2:1 randomized, double-blind, placebo-controlled study to assess the safety and efficacy of AER002 to treat Long COVID (LC).

The study will enroll approximately 30 participants who meet the WHO LC criteria. Participants will be enrolled at a single center and randomized 2:1 to receive AER002 1200mg or placebo (20 to AER002 and 10 to placebo). Evaluations will take place at baseline and at timepoints up to 1-year post-infusion.

Screening data will be reviewed to determine subject eligibility. Subjects who meet all inclusion criteria and none of the exclusion criteria (see study protocol) will be entered into the study.

The following treatment regimens will be used:

Route	Planned Dose	Dose	mL	Total Dose	Total mL
Intravenous (IV)	AER002	1200 mg	24	1200 mg	24
	Placebo	NA	24	NA	24

The total duration of subject participation will be approximately 12 months. The study visits will occur at screening, baseline, infusion and days 15, 30, 90, 180 and 360 (D15, D30, D90, D180, D360, respectively) following infusion.

### 2.2. Study Endpoints

#### Efficacy Endpoints

- The change in PROMIS-29 Physical Health and Mental Health summary scores comparing Baseline to D90.
- Change in other assessments (EuroQoL Quality of Life, CNS Vital Signs, DASI, COMPASS-31, WHO-DAS 2.0, PGIC, ECog-39, dysautonomia (COMPASS-31), DSQ-PEM, 6 Minute Walking Test, Active Stand Test performance) between Baseline and at D30, D90, D180, and D360.

- Percentage of participants with no detection of SARS-CoV-2 plasma remnants (i.e., viral detection by reverse transcriptase-polymerase chain reaction (RT-PCR) and Spike protein fragments) comparing baseline to D30, D90, D180, and D360.
- Proportion with reduction in inflammatory markers (e.g., interleukin-6 (IL-6), C-reactive protein (CRP) at Baseline and at D30, D90, D180, and D360.

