## PROTOCOL SYNOPSIS

TITLE	AN EXPLORATORY, RANDOMIZED, DOUBLE-BLIND PLACEBO-CONTROLLED STUDY TO ASSESS THE SAFETY OF AN ANTI-SARS-COV-2 MONOCLONAL ANTIBODY AND RESPONSE TO TREATMENT IN INDIVIDUALS WITH LONG COVID (OUTSMART-LC) (COVID-19)
SPONSOR	University of California, San Francisco
FUNDING ORGANIZATION	University of California, San Francisco Aerium Therapeutics
NUMBER OF SITES	1
RATIONALE	There are currently no widely accepted therapies for Long COVID. Viral antigen persistence is one of the key mechanisms that might drive this condition. Clearance of viral antigen or infected cells with a SARS-CoV-2 monoclonal antibody may lead to symptomatic improvement in people with Long COVID.
STUDY DESIGN	Randomized, double-blind, placebo-controlled study.
PRIMARY OBJECTIVE	To evaluate the safety and tolerability of AER002 in individuals who are experiencing Long COVID.
SECONDARY OBJECTIVES	
 
1. Describe the ability of AER002 to affect virologic markers of chronic SARS-CoV-2 infection.
 
2. Describe the ability of AER002 to improve PASC outcomes.
 
3. Describe the ability of AER002 to reduce post-COVID inflammation.
 

NUMBER OF SUBJECTS	30
SUBJECT SELECTION CRITERIA	
Inclusion Criteria:
 
 
1. Male, female, or transgender ≥18 years of age at Screening.
 
2. Enrolled or willing to enroll and complete at least 1 visit in the UCSF Long-term Impact of Infection with Novel Coronavirus (LIINC) study. Any adult who has been infected with SARS-CoV-2 or has ever received or is eligible to receive a SARS-CoV-2 vaccination, does not have chronic anemia, and who is able to provide written informed consent, is eligible to participate in LIINC.
 
3. History of confirmed acute SARS-CoV-2 infection, whose initial infection meets criteria as outlined below: 
 
a. Report of a positive nucleic acid amplification test (NAAT) and/or a positive SARS-CoV-2 antigen rapid diagnostic test (RDT). Written proof of the test will be
 
 
 

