The presence of viral RNA and proteins in the post-acute phase does not necessarily represent ongoing viral replication and viral RNA can persist even in the absence of culturable virus. Viral persistence represents a spectrum which includes the persistence of viral proteins, degraded or partial RNA fragments, and full-length replication-competent RNA. While each of these components could

stimulate immune responses, the optimal biological target is dependent on which components are driving the disease process. For example, if the presence of SARS-CoV-2 antigen represents active viral replication, targeting this with antivirals such as protease or RNA polymerase inhibition would be an effective approach. However, these agents have several disadvantages including complex administration, drug-drug interactions, and unattractive adverse effect profiles. Furthermore, if no active viral replication is occurring and only sub genomic RNA or protein is present, these therapies would not be effective. Instead, mAbs which act by neutralizing the spike protein of SARS-CoV-2 might be more attractive. By binding spike, which exists on the cell surface and can sometimes be detected in plasma of those with LC, these Abs could have beneficial effects through neutralization of proteins and virions, opsonization of virions and infected cells, and potentially the induction of Ab- or complement-mediated cellular cytotoxicity if viral proteins are expressed on the cell surface. These agents typically have more favorable dosing and side effect profiles, and have the added benefit of clearing infected cells.

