## **9.3 Research Laboratory Measurements**

### **9.3.1 Plasma Measures of Viral Persistence**

Plasma levels of SARS-CoV-2 antigens (Spike, nucleocapsid, etc.) may be performed in collaboration with research laboratories to evaluate the effect of mAb therapy on measures of viral persistence.

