### **9.3.3 Pharmacokinetic (PK) analyses**

Blood samples for determination of serum concentrations of AER002 will be collected at following timepoints:

- Pre-dose
- Post dose:
  - 1 hour (acceptable +/- 10 min)
  - D15 (acceptable +/- 3 Days)
  - D30 (acceptable +/- 5 Days)
  - D90 (acceptable +/- 14 Days)
  - D180 (acceptable +/- 14 Days)
  - D360 (acceptable +/- 28 Days)

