#### **4.3.3 Laboratory Measures**

- Change from Baseline to D15, D30, and D180 in CRP, ESR, D-Dimer, and Fibrinogen
  - The primary estimand for these outcomes is the difference in mean change from baseline.
  - These continuous outcomes will be analyzed as described in [Section 3.5](#) , i.e. using a mixed effect model for repeated measurements.
- Percentage of participants with no detection of SARS-CoV-2 plasma remnants (i.e., viral detection by reverse transcriptase-polymerase chain reaction (RT-PCR) and Spike protein fragments) compared to Baseline through D180.

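### The virologic endpoint includes undetectable plasma Spike, which the study antibody binds, and the plan has no way to tell clearance from possible masking of Spike-only positives

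*Combined protocol and SAP*

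**What the plan says.** SAP 2.2 lists among the efficacy endpoints "Percentage of participants with no detection of SARS-CoV-2 plasma remnants (i.e., viral detection by reverse transcriptase-polymerase chain reaction (RT-PCR) and Spike protein fragments", comparing baseline with D30, D90, D180 and D360. SAP 4.3.3 carries the endpoint as an exploratory laboratory measure through D180 ("Percentage of participants with no detection of SARS-CoV-2 plasma remnants"), with no estimand or method under the bullet. Protocol 5.1 has the same definition. None of these places says whether a participant must be negative on both tests or on either one to count as not detected.

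On mechanism, Protocol section 2 explains the choice of drug class: "mAbs which act by neutralizing the spike protein of SARS-CoV-2 might be more attractive". It expects benefit to arise "By binding spike, which exists on the cell surface and can sometimes be detected in plasma of those with LC". The synopsis states the intended effect: "Clearance of viral antigen or infected cells with a SARS-CoV-2 monoclonal antibody may lead to symptomatic improvement".

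On measurement, Protocol 9.3.1 says only that "Plasma levels of SARS-CoV-2 antigens (Spike, nucleocapsid, etc.) may be performed in collaboration with research laboratories". It gives no assay format, no distinction between free and total Spike, and no statement on drug tolerance. Protocol 9.3.3 provides for drug levels: "Blood samples for determination of serum concentrations of AER002 will be collected at following timepoints", namely pre-dose, 1 hour, D15, D30, D90, D180 and D360. No section of either document links those concentrations to the Spike result.

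**The concern.** The analyte in the endpoint is the drug's own target. After dosing, a Spike result can turn negative because Spike has gone, or because Spike is present with antibody attached and the assay no longer sees it. The first is the effect the trial hopes for. The second would be a measurement artefact.

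Randomisation and blinding do not protect against this. Only the active arm receives AER002, so any masking would be differential and would run towards apparent efficacy.

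An effect on virologic markers is the first secondary objective in Protocol 3.2. Protocol 15.6 and SAP 2.4 say the study uses AER002 as a probe to decide whether there is a signal worth pursuing. A spurious virologic signal would bear on that decision.

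**Working it through.** **Inputs.** Allocation 20 AER002 to 10 placebo (Protocol 8.1). Antigen positivity at entry 25%, falling to below 1% on treatment, with a stated power of 62% (Protocol 15.6). Two-sided 0.05 Fisher exact test for antigen detection (Protocol 15.4). The documents give no masking rate, so the share masked, m, is varied from 0 to 1.

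**Step 1: the plan's own figure.** Pooled normal approximation with placebo 0.25 and AER002 0:
- pooled proportion = 2.5/30 = 0.0833
- null SE = √(0.0833 × 0.9167 × (1/10 + 1/20)) = 0.1070
- alternative SE = √(0.25 × 0.75/10) = 0.1369
- z = (0.25 − 1.96 × 0.1070)/0.1369 = 0.294, so power is about 61.5%

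This reproduces the stated 62%. At exactly 1% on treatment the same formula gives 56.5%. Enumerating the planned Fisher test gives 47.4% at 0% and 42.6% at 1%.

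**Step 2: masking with no true clearance.** Assume true positivity stays at 25% in both arms, every positive is Spike-only (RT-PCR negative), and a share m of AER002-arm positives becomes undetectable. Apparent positivity on AER002 is 0.25 × (1 − m). The chance of a significant result is the sum, over a positives on placebo and b on AER002, of Bin(a; 10, 0.25) × Bin(b; 20, 0.25(1 − m)) for those tables where the two-sided Fisher p is at most 0.05.

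| Share masked, m | Apparent positivity on AER002 | Chance of significance |
|---|---|---|
| 0 | 25% | 2.7% |
| 0.25 | 18.75% | 4.7% |
| 0.50 | 12.5% | 10.6% |
| 0.75 | 6.25% | 23.3% |
| 0.96 | 1% | 42.6% |
| 1 | 0% | 47.4% |

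**Step 3: hand check of the last row.** With no positives on AER002, 3/10 on placebo gives p = C(10,3)/C(30,3) = 120/4060 = 0.030, and 2/10 gives p = C(10,2)/C(30,2) = 45/435 = 0.103. The test therefore rejects when placebo has three or more positives: 1 − (0.0563 + 0.1877 + 0.2816) = 0.474. The expected number of AER002 positives to be hidden is 20 × 0.25 = 5.

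**Step 4: dependence on the 25%.** That rate is the protocol's assumption. If positivity were 50%, the chances at 0, 50, 75 and 100% masking would be 2.6, 23.1, 54.8 and 94.5%.

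**Step 5: comparison.** At m of 0.96 to 1 the distribution of results is that of the protocol's success scenario (25% to below 1%), although nobody has cleared anything. This follows by construction. What it shows is that the endpoint alone carries no information that separates the two explanations in Spike-only positives.

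**The case against.** The strongest objection is that the key premise is not in the documents. They say the antibody binds Spike. They do not say that bound Spike is less detectable. No half-life for AER002 is given, so drug presence at D90 to D360 cannot be judged either. Protocol section 2 also acknowledges that people with robust circulating antibodies may fail to clear antigen, and reports antigen at least intermittently detectable in many people with Long COVID. Antibody presence cannot simply be equated with non-detection. This stands, and the point is therefore conditional. It does not remove the gap, because participants' own antibodies are present in both arms whereas AER002 is in one.

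Second, a reader might infer that RNA and Spike are irrevocably merged. The documents do not support that. No combination rule is stated, Appendix 1 schedules viral-persistence markers and PCR/genotyping as separate rows, and Protocol 15.4 treats antigen detection by itself. If either positive counted as detected, an RNA-positive participant would stay detected whatever happened to Spike. Full confusion applies only to Spike-only positives.

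Third, the illustration is a worst case. It takes every positive as Spike-only, holds placebo positivity at 25% although detection is described as intermittent, and uses a single-visit Fisher test. SAP 3.3 sends longitudinal binary outcomes to a GEE model, and SAP 4.3.3 names no test, so the percentages may not describe the analysis finally run.

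Fourth, the stakes are limited. The SAP lists the analysis as exploratory, and SAP 2.4 no longer carries the antigen power statement. The primary safety outcome, the PROMIS-29 outcome and the baseline-antigen subgroup are untouched.

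Finally, a reader might conclude that the virologic finding should rest on RNA and nucleocapsid alone. That goes too far. Nucleocapsid is optional in Protocol 9.3.1, and Protocol section 2 counts neutralisation of protein among the possible benefits, so a real effect confined to Spike would be discounted in advance.

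**Conclusion.** The concern holds as a gap in specification and interpretation. The endpoint includes non-detection of the drug's own target. The documents give neither the assay's tolerance to AER002 nor a rule for post-dose Spike negatives, and the concentrations that would help are collected but not used for this purpose. Any masking would favour AER002.

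The size is unknown. Under the stated assumptions the chance of a false significant result rises from 2.7% without masking to 11% at half, 23% at three quarters and 47% at full masking. A quarter masked has little effect (4.7%).

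The documents do not support the stronger reading that AER002 does hide Spike, or that masking of any degree would look the same as the targeted effect. That equivalence holds only at about 96 to 100% masking of Spike-only positives. The change is a cheap improvement to an exploratory analysis that serves a stated secondary objective.

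**What to change.** In SAP 2.2 and 4.3.3:

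- Report RT-PCR and Spike as separate outcomes at each visit, and nucleocapsid where it is measured. If a combined outcome is kept as well, state its rule.
- Tabulate Spike detection against the AER002 concentration from the same visit.
- State that Spike non-detection will not be interpreted as clearance while AER002 is measurable, unless the laboratory documents that the assay is unaffected by the drug.
- Keep Spike in the virologic conclusion, with that qualification, and do not restrict the conclusion to RNA and nucleocapsid.
- Name the analysis method (Fisher or GEE), since the 4.3.3 bullet has none.

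The cost is SAP wording, a few tables and a request to the laboratory. The drug-level samples are already scheduled at the same follow-up visits as the viral-persistence markers. The downside is small counts: 25% of 30 is 7.5 expected positives in all, fewer per analyte, so each component will be imprecise and Spike results will be read more cautiously.
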